4.1 Study Design

Post-market, real world, prospective, multi-center study that will enroll approximately 800 subjects at up to 60 global sites.

4.2 Study Objectives/Endpoints

4.2.1 Primary Endpoints

Efficacy:

- Adequate occlusion defined as Raymond-Roy Occlusion Class I and II at final follow-up

Safety:

- SAEs within 24 hours post-procedure
- Device-related SAE up to 7 days or discharge

4.2.2 Secondary Endpoints

Efficacy:

- Immediate post-procedure occlusion rates
- Retreatment rate at final follow-up
- Aneurysm Occlusion Raymond I post treatment
- Aneurysm Occlusion Raymond I at final follow-up
- Aneurysm recanalization or progressive thrombosis from post procedure to final follow-up

Safety:

- Major ipsilateral stroke
- Device related SAE at final follow-up
- All-cause morbidity and mortality

5. Study Population

5.1 Inclusion Criteria

1. Patient age \geq 18 years
2. Patient having embolization of intracranial aneurysms
3. WAVE Extra Soft Coil is the final finishing coil
4. Penumbra SMART COIL System accounts for at least 75% of total number of coils implanted
5. Informed consent obtained per IRB/EC requirements

5.2 Exclusion Criteria

1. Life expectancy less than 1 year
2. Patient previously enrolled in the SURF Study
3. Known multiple intracranial aneurysms requiring treatment during index procedure
4. Patient is unwilling or unable to comply with protocol follow up schedule and/or based on the Investigator's judgment the patient is not a good study candidate
5. Participation in an interventional drug or device study that may confound the results of this study

[figure not shown]
6. Study Procedures

6.1 Overview of Study Flow

Patients ≥ 18 years of age having embolization of intracranial aneurysms should be assessed for eligibility. All sites will keep a screen failure log of all potential study candidates who are screened and not enrolled or screened, consented, and not enrolled. Reason(s) for exclusion will be recorded. Screening information will be reported in Electronic Data Capture System (EDC).

Recruitment rates will be tracked over time for each site. The actual recruitment rates will be useful for planning further clinical trials and determining the widespread impact of the therapy.

Figure 1: Study Flow

*For sites in North America, ICF may be obtained up to 2 days post-procedure, but prior to discharge

6.2 Study Visits

Subjects enrolled in this study will follow the visit schedule below and will continue to receive routine practice/ standard of care treatment. Procedure is day 0 for determining follow-up visit dates.

- Screening & Baseline
- Procedure
- 7 Day and/or Discharge
- 1 Year Follow-Up ± 90 Days

6.3 Recruitment

The target population are subjects ≥ 18 years of age presenting with an intracranial aneurysm(s). No study specific screening tests or procedures are required for enrollment in the study. Standard of care evaluations will be used to confirm eligibility.

Potential study participants and/or their legal authorized representative (LAR) will be identified by the study team at each site to obtain consent and determine eligibility. The study allows for enrollment up to 800 subjects at up to 60 global sites.

6.4 Screening and Enrollment

The subject will be clinically evaluated in the same manner as any patient presenting with intracranial aneurysm(s). The medical history screen, available clinical/neurological exams obtained, and imaging information per institutional routine care will be evaluated to determine patient eligibility.

Pre-procedure angiography will be performed per institutional standard of care and will allow to define aneurysm location, size and best treatment strategy.

Patients will be considered enrolled once informed consent is obtained per IRB/EC, the index procedure is complete, and all eligibility is confirmed. Patients who fail to meet entry criteria pertaining to coil selection will be considered a screen fail.

6.5 Informed Consent

The Investigator or designee will obtain written informed consent from the subject or LAR using the current IRB/EC approved consent form per IRB/EC policy. For sites in North America, patients who have had an index procedure with SMART Coils and all eligibility is confirmed, may be consented up to 2 days post-procedure but prior to discharge. For sites outside of North America, the informed consent signature process will be described in Informed Consent Form and will be applied per local Ethics Committee approvals.

All informed consent documents used under this protocol will be consistent with applicable elements of EN ISO 14155:2011, Clinical investigation of medical devices for human subjects – Good Clinical Practice and 21 CFR Part 50, Protection of Human Subjects, and will be approved by the site's reviewing IRB/EC prior to study initiation.

Any modification to the sample informed consent form made by the study site must be approved by the Sponsor and the IRB/EC before use. Each study site will provide the Sponsor with a copy of the IRB/EC approved consent forms. Informed consent completion will be monitored regularly by the Sponsor.

6.6 Screening and Baseline Evaluation

All assessments are to be conducted in accordance with routine care at each participating hospital; the following data will be collected but is not limited to:

- Demographics
- Vital signs
- Review of medical history

- Baseline mRS
- If a patient has a SAH at baseline, the Hunt and Hess score will be collected

6.7 Procedure

All procedures are to be conducted in accordance with routine care at each participating hospital and the Instructions for Use for each device used.

At a minimum, the following information will be captured in the Case Report Form (CRF) for the target aneurysm, data will not be captured for ancillary aneurysms treated during the index procedure:

- Sedation
- Type of aneurysm
- Size of aneurysm
- Aneurysm location
- Procedural information
- Devices used
- Aneurysm occlusion grade
- Adverse event review
- Angiography

Procedural angiography will be performed per institutional standard of care. Imaging will be uploaded and sent to an Imaging Core Laboratory to make a final determination on aneurysm occlusion rate.

6.8 7 Day and/or Discharge

The 7 day and/or discharge visit should be done within 1 day prior to discharge or at day 7, whichever occurs first. All assessments are to be conducted in accordance with routine care at each participating hospital, the following data will be collected but is not limited to:

- Vital signs
- mRS
- Adverse event review

In addition to the assessments above the following will be collected at discharge:

- The location that the subject is discharged to and the date of discharge
- If any adverse events occurred, it will be reported on the Adverse Event Form

6.9 Final Follow-Up (1 Year \pm 90 Days)

All assessments are to be conducted in accordance with routine care at each participating hospital, the following data will be collected but is not limited to:

- Aneurysm occlusion grade
- Vital signs
- mRS
- Retreatment information
- Adverse event review
- Angiography*

*Angiography will be performed per institutional standard of care. DSA, CTA, or MRA are accepted for imaging modality. Images will be sent to an Imaging Core Laboratory to make a final determination on aneurysm occlusion rate. If both DSA and MRA are available, then both imaging modalities should be submitted for Core Laboratory review.

Table 2: Schedule of Assessments

ACTIVITY	SCREENING & BASELINE	PROCEDURE	7-DAY AND/OR DISCHARGE	FINAL FOLLOW-UP (1 YEAR ± 90 DAYS)
Written Informed Consent	X ¹			
Demographics	X			
Medical History	X			
Vitals	X		X	X
mRS	X ²		X	X
Hunt & Hess	X ³			
Procedure		X ⁴		
Occlusion Grading		X		X ^{4,5,6}
Adverse Event Review		X	X	X

¹ For sites in North America, patients who have had an index procedure with SMART Coils and all inclusion/exclusion confirmed, may be consented up to 2 days post procedure but prior to discharge

² Baseline mRS is based on subject status prior to the index procedure

³ For patients presenting with SAH

⁴ Imaging should be uploaded into Image Management System within 14 days

⁵ Occlusion Grading and other datapoints will be collected if retreatment occurs prior to study exit

⁶ If both DSA and MRA are performed as part of standard of care follow-up, then both imaging modalities should be submitted for Core Laboratory review

7. Investigator Responsibilities

7.1 Institutional Review Board / Ethics Committee Approval

Prior to enrolling patients into the study, the investigator will ensure that proper Institutional Review Board (IRB)/Ethics Committee (EC) approval is obtained in accordance with applicable local laws and regulations. The IRB/EC shall approve all study documents as appropriate, including but not limited to the final protocol, amendments to the protocol, Instructions for Use (where applicable), Investigator Brochure (where required), and the informed consent.

The investigator will report to the Sponsor or designee immediately if the approval to conduct the investigation is withdrawn by the IRB/EC or Competent Authority. The report will include a complete description of the reason(s) for which approval was withdrawn.

7.2 Informed Consent

The investigator is responsible for ensuring that a signed and dated informed consent is obtained in accordance with Section 6.5 of this protocol and according to country and local requirements.

7.3 Adherence to Protocol/Amendments and Applicable Law

The investigator is responsible for overseeing, ensuring that the study is conducted, and completing the study according to this protocol and in accordance with the relevant aspects of EN ISO 14155:2011, Declaration of Helsinki, along with any conditions imposed by the reviewing IRB or EC, and all other applicable regulations. The investigator shall approve and adhere to this protocol and any amendments that arise during the course of the study.

It is the investigator's responsibility to ensure that the staff assisting with the study have the appropriate qualifications, are fully instructed on the study procedures, and will respect study confidentiality.

7.4 Case Report Form Completion

The Investigator and study staff shall complete the case report forms (CRFs) associated with this study. Subject numbers shall be used to identify individual participants in this study. The CRFs should be a complete and accurate record of subject data collected during the study according to relevant aspects of I.S. EN ISO 14155, 21 CFR 11, Electronic Records; Electronic Signatures and GCP requirements. It is the Investigator's responsibility to ensure the quality of the data collected and recorded is appropriate and collected in accordance with GCP and all applicable regulations. Data entry will be performed by the study site(s). Investigators are responsible for completion and timely submission of data to Penumbra, Inc. Every reasonable effort should be made to complete data entry within 7 business days of data collection.

7.5 Image Upload

Images from Immediate Post Procedure and Final Follow-Up visit may be uploaded to an image management system for Core Lab review. Instructions for image collection and upload will be provided. Study staff shall ensure that no images contain any personally identifying information about the subject or study site (e.g. Physician name, Institution name, patient name, etc.).

Sites will be provided with instructions for how images should be collected and submitted within 14 days of the acquisition of the required imaging. If the site is unable to provide the images within this time frame, the appropriate Sponsor contact should be notified.

7.6 Reporting

The investigator will be responsible for reporting the following:

7.6.1 Adverse Events

Adverse events (AE) must be recorded by the Investigator on the CRFs and will be monitored during the study. Only adverse events related to the procedure or device, and all SAEs will be collected starting at procedure through discharge for enrolled subjects. After discharge only neurological SAEs will be collected. Additional information for Symptomatic Intracranial Hemorrhage and Ischemic Stroke will be collected on Event of Interest CRFs.

Minimum requirements of data to be recorded are: Adverse event term, event start date, seriousness, action taken, outcome and procedure / device-relatedness or causality.

In order to ensure prompt reporting of AEs, all reportable AEs (as well as all related study data) are required to be entered into the EDC in a timely manner. Any suspected UADEs should be reported immediately by calling the Sponsor. All device related SAEs should be reported in the EDC within 72 hours of the site staff first being made aware of the occurrence of the SAE. If the EDC is unavailable, an email can be sent to Penumbra.

The Investigator must report adverse events to the IRB/EC according to local requirements. The investigator is responsible for reporting time frames and complying with local or national requirements. In addition, the investigator will report to the sponsor and IRB/EC any device deficiencies that could have led to a SAE, if required by national regulations or by local authorities.

For the purpose of reporting within this protocol, pre-existing conditions or planned procedures for pre-existing conditions are not reportable as AEs unless there is worsening of the condition with an increase in severity or frequency during the course of the study. All deaths will be reported regardless of causality. When reporting a death, the primary condition or diagnosis that contributed to the fatal

outcome should be reported as a SAE with an outcome of death. Only a single cause of death should be reported in EDC. If the cause of death is unknown, report “unknown cause of death” as a SAE.

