2.4 Indications

The Penumbra SMART COIL System is indicated for the embolization of:

- Intracranial aneurysms
- Other neurovascular abnormalities such as arteriovenous malformations and arteriovenous fistulae
- Arterial and venous embolizations in the peripheral vasculature

Embolization coils perform their intended function by volume filling of the aneurysm sac or target location. Achievement of aneurysmal occlusion is based on volume filling of the aneurysm, causing blood flow diversion from the aneurysmal sac to the parent artery, leading to secondary clot formation and organization within the target location.

The Penumbra SMART COIL System originally received the CE Mark in December 2014, FDA 510(k) clearance in March 2015, and Health Canada approval in October 2015.

3. Risk Analysis

A thorough risk analysis was performed as part of design control requirements of the Quality System Regulation (21 CFR 820). The current potential complications listed on the Instructions For Use (IFU) label include the following:

- acute occlusion
- air embolism
- allergic reaction and anaphylaxis from contrast media
- aneurysm rupture
- arteriovenous fistula
- coagulopathy
- infection
- intima dissection
- intracranial hemorrhage
- ischemia
- myocardial infarction
- neurological deficits including stroke
- parent artery occlusion

- coil herniation into parent vessel
- death
- device malfunction
- distal embolization
- emboli
- embolic stroke and other cerebral ischemic events
- false aneurysm formation
- hematoma or hemorrhage at access site of entry
- incomplete aneurysm occlusion
- peripheral thromboembolic events
- post-embolization syndrome
- premature device detachment
- recanalization
- renal failure
- respiratory failure
- revascularization
- thromboembolic episodes
- vessel spasm, thrombosis, dissection, or perforation

Potential complications associated with cerebral endovascular coiling procedures are similar to other angiographic and coiling procedures and may include:

- Allergic reaction to contrast agents
- Access site complications
- Infections
- Pseudoaneurysms
- Arterial dissection
- Parent vessel occlusion
- Thromboembolism (or other embolism)
- Aneurysm perforation (ruptured and unruptured)
- Rebleed
- Procedure-related morbidity
- Procedure-related mortality
- Coil migration

4. Study Overview

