10.2 Secondary Safety Analysis

For the secondary safety endpoints, frequency counts, percentages, and two-sided 95% Wald confidence intervals will be reported using the ITT population:

- **Major ipsilateral stroke:** The percentage of patients who experience major ipsilateral stroke adverse event(s), as defined in the SURF study protocol.
- **Device related SAE at final follow-up:** The percentage of patients who experience serious adverse event(s) with probable or definite relationships to the SMART Coil System from the date of procedure (day 0) through the final follow-up visit at 1 Year \pm 90 Days from the date of procedure.
- **All-cause morbidity and mortality:** The percentage of patients who experience either of the following events:
 - **All-cause morbidity:** mRS 3 to 5 at the final follow-up evaluation or worsening of mRS by 2+ points the date of procedure (day 0) through the final follow-up visit at 1 Year \pm 90 Days from the date of procedure. If the final follow-up mRS is missing, mRS as assessed at the 7-day and/or discharge visit will be substituted.
 - **All-cause mortality:** Death for any reason from the date of procedure (day 0) through calendar day 365

Adverse events occurring after the final follow-up visit at 1 Year \pm 90 Days and deaths occurring after day 365 will be separately tabulated and not included in endpoint and adverse event rates.

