10.3 Analysis of Adverse Events

In the SURF study, only device-related or procedure-related adverse events and serious adverse events (SAEs) will be collected from procedure through discharge. After discharge, only neurological SAEs will be collected. Additional information for Symptomatic Intracranial Hemorrhage and Ischemic Stroke will be collected on Event of Interest case report forms.

Frequency counts and percentages will be provided for all reportable adverse events and broken down as well based on relationships to the device and procedure. Reportable adverse event data will be listed for each patient, including the type of event/verbatim term, start date, seriousness, action taken, outcome, and causality (if appropriate). The onset of adverse events will also be shown relative (in number of days) to the date of procedure.

The specific categories analyzed will be those that are reported by at least three (3) percent of the patients. As there is no CEC for this study, all adverse events will be reported based on the assessment from the clinical study sites.

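### The one-year device-related SAE endpoint is wider than the rule for collecting SAEs after discharge, so its reported rate is a lower bound on what its label says

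*Combined protocol and SAP*

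**What the plan says.** Protocol 4.2.2 lists "Device related SAE at final follow-up" as a secondary safety endpoint. SAP 10.2 makes it the percentage of patients with SAEs "with probable or definite relationships to the SMART Coil System from the date of procedure (day 0) through the final follow-up visit"; the window for that visit is 1 year ± 90 days. Neither place limits the endpoint by body system.

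Collection is narrower. Under protocol 7.6.1, all SAEs, and AEs related to the procedure or device, are collected from the procedure through discharge. Then: "After discharge only neurological SAEs will be collected". SAP 10.3 repeats the limit: "After discharge, only neurological SAEs will be collected". Protocol 7.6.1 also contains three statements that reach past it:

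- On unanticipated effects: "Any suspected UADEs should be reported immediately by calling the Sponsor".
- On deaths: "All deaths will be reported regardless of causality", and the cause is entered as an SAE.
- On timing: "All device related SAEs should be reported in the EDC within 72 hours", counted from when site staff learn of the event, with no end date and no restriction to neurological events.

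**The concern.** The numerator of the endpoint is wider than the set of events that sites are told to collect. A patient whose only device-related SAE is of an uncollected type counts as having had no event. The denominator is the full ITT population, so on the restrictive rule this error can only lower the rate.

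A reader of the final report would take the figure as all device-related SAEs to about one year. Protocol 10.15 foresees publication and use in regulatory submissions. The planned sensitivity analyses would not show the problem: SAP section 12 imputes only for the primary endpoints, and an event that was never collected does not appear as a missing value. If sites also read the 72-hour sentence differently, they may enter different events for the same endpoint.

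**Working it through.** **Which events fall in the gap.** For an SAE after discharge that is graded probable or definite for the device:

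| Type of event | In the endpoint (SAP 10.2) | Collected or reportable (protocol 7.6.1) |
|---|---|---|
| Neurological | yes | yes |
| Fatal, any type | yes | yes, as a death |
| Non-fatal, non-neurological, unanticipated | yes | by telephone to the sponsor, as a suspected UADE |
| Non-fatal, non-neurological, anticipated | yes | no |

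The last row is the gap. The UADE definition in protocol 7.6.2.1 covers effects not already identified in the protocol or instructions for use, so it does not reach anticipated events.

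**The 72-hour sentence.** It stands in a paragraph about prompt entry of reportable events, which favours reading it as a deadline for events already in scope. The gap then stands. If it is a duty to enter every device-related SAE at any time, it contradicts the neurological limit in the same section, and SAP 10.3 carries only the limit. Both readings call for a correction.

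**Other routes.**

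- Device deficiencies go through the commercial complaint process (protocol 7.6.3).
- Retreatment data (6.9) serve a different endpoint.
- The adverse event review at the final visit (6.9, Table 2) does not say which events it covers.
- The Medical Monitor reviews what has been reported (7.6.2).
- Copies of IRB/EC correspondence go to the sponsor (9.1), and the sponsor evaluates reports that it receives or finds in monitoring (8.3).

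These may reveal some of the missing events. None requires that they be entered in the EDC or counted.

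**Size.** The documents give no planned rate for this endpoint, so there is no figure of the plan's own to reproduce. The nearest is the primary device-related SAE endpoint, 22/800 (protocol 10.2, SAP section 2):

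- Rate: 22/800 = 2.75%.
- Wald half-width: 1.96 × √(0.0275 × 0.9725 / 800) = 1.13 percentage points.
- Interval: 1.62% to 3.88%, which agrees with the stated 1.6% to 3.9%.

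That endpoint closes at the earlier of day 7 or discharge. Under the planning assumption, 22 is therefore a floor for the one-year count. Against this scale:

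- One missed patient: 1/800 = 0.125 points.
- One to five missed patients (an assumption, for illustration only): 0.125 to 5/800 = 0.625 points.
- Number needed to exceed the half-width: 1.133 / 0.125 = 9.07. Nine patients (1.125 points) stay inside it and ten (1.25 points) exceed it. A larger count widens the interval (38/800 has a half-width of 1.47 points), so ten is a minimum.
- Suppose 8 further patients have their first device-related SAE after discharge (also assumed). The true rate is 30/800 = 3.75%. The reported rate is 26/800 = 3.25% if half of the 8 are missed and 22/800 = 2.75% if all are.

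A missed event in a patient who already counts changes nothing.

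**Primary endpoints.** The device-related one ends no later than discharge (SAP 10.1). The 24-hour one ends on the calendar day after the procedure, which only a very early discharge could overlap. The efficacy endpoint uses imaging.

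**The case against.** The strongest reply is that the neurological limit looks deliberate. Both documents state it alike, the device is an intracranial coil, and many of its related SAEs would be neurological. To fall in the gap, an event must be after discharge, non-fatal, non-neurological, anticipated and graded probable or definite for the device. Few may qualify. That stands as an argument about size. It does not make the endpoint definition match the collection rule.

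A reader might infer that nothing central would catch or even out such events, since SAP 10.3 reports AEs on site assessment without a CEC. The documents do not support this. A CEC adjudicates events; consistent entry is served by sponsor training (protocol 8.1), monitoring with source checks (8.4.3), EDC queries (8.5) and the Medical Monitor (7.6.2). What stands is narrower: none of these obliges a site to enter an event that the collection rule leaves out.

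A reader might also pick "peripheral thromboembolic events" from the complication list in protocol section 3 as a plain example of a lost event. That list covers a system also indicated for peripheral embolization (2.4), and nothing shows that such an event is likely late after intracranial coiling. The text supplied contains no definition of a neurological SAE, so the excluded set could be smaller or larger than it seems.

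Finally, the planned 10% attrition (80 of 800) may limit one-year ascertainment more than this gap does. That is fair, but attrition is foreseen and reported in the disposition; this gap is not disclosed.

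**Conclusion.** The mismatch is in the current text of both documents. On the restrictive collection rule, the reported rate is a lower bound on what the label promises. The alternative reading of the 72-hour sentence replaces the gap with a contradiction that also has to be settled.

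The shortfall cannot be computed from the documents. It is 0.125 points per missed patient, on the assumption that 800 are enrolled and analysed, and it is probably small. The comparison with 1.13 points borrows the interval of a different endpoint, for scale only. It would be tempting to conclude that the trial materially understates device harm; the documents give no post-discharge rate that would support this. The point concerns one secondary endpoint in a study whose analyses are described as descriptive (protocol 10.1). It should be corrected because the error runs in one direction and the remedy is mainly wording.

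**What to change.** Before database lock, reconcile SAP 10.2 with protocol 7.6.1 and SAP 10.3:

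1. Restate the endpoint in SAP 10.2 as SAEs graded probable or definite for the SMART COIL System: all types through discharge, then neurological or fatal SAEs so graded through final follow-up. Apply the same relatedness grade to every component, so that deaths from other causes are not counted.
2. State in the SAP and the report that this is narrower than the label in protocol 4.2.2 and is a lower bound for all device-related SAEs.
3. Tabulate separately any other post-discharge device-related SAEs in the EDC, including UADEs, and give a second rate that includes them. SAP 10.2 already tabulates late events apart.

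The cost is SAP and report wording, which SAP section 13 allows, plus one listing. The downside is a narrower stated endpoint, and events that sites did not enter are not recovered. The protocol text stays as written, so the report must explain the difference.

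Alternatively, if the protocol is being amended anyway, state in 7.6.1 and SAP 10.3 that all device-related SAEs are collected through final follow-up. This also settles the 72-hour sentence. It needs IRB/EC approval at up to 60 sites and leaves mixed ascertainment between patients followed under the two rules, which should be reported. It needs no new visit, because adverse event review is already scheduled at final follow-up.
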